15.1.3 Publication and Presentation Policy Roles and Responsibilities

Roles and Responsibilities of Writing Team members include:

Lead Author	
 Submitting/revising the proposal abstract Identifying interested potential co-authors and making the final decision on which have satisfied the ICMJE requirements Identification of a realistic submission date goal Progress on meetings and paper drafts Developing the first draft of the paper Coordinating with appropriate staff to integrate data findings Scheduling and facilitating calls/meetings, as needed Distributing drafts to the writing team for input Making sure the final draft is copy-edited ([name] to assist)
Co-Author	
 Contributing ideas and references, not just copy-editing Responding to each draft distribution within the requested time
Mentor	When an investigator is the first author but has limited experience with publication, they should identify a mentor who can coach and/or support them in the development and completion of the manuscript in a timely way
Co-PIs & Executive Team	Responsible for approving proposal abstracts, prioritizing papers, identifying co-authors, and monitoring progress.

15.1.4 Abstract for Proposed Publications and Presentations

Abstracts for proposed publications and presentations should describe the following elements:

1. Descriptive title and date
2. Main goal, question, or hypothesis to be addressed in the paper
3. Brief rationale and description of analyses
4. Data needed
5. Lead author and tentative co-authors
6. Audience and journal targeted
7. Target date for submission

15.2 Key Journal Publication milestones

1. Proposal submission to the PIs
2. Proposal approval

3. First draft to co-authors
4. Submission to a journal
5. Journal decision
6. Resubmissions
7. Acceptance
8. Publication

15.3 Making Research findings Publicly Available

15.3.1 Public Summary of Findings

Besides our primary outcomes paper, we will also produce a summary of research findings for patients and the general public in order to convey our findings in a “comprehensible and useful manner to patients and providers to use in making health care decisions.” PCORI and our patient co-investigators and advisory group will help us to develop the summary and ensure that it is available in public-access format.

15.3.2 Public Access to Journal Articles

An electronic copy of the final peer-reviewed publication of our primary outcomes will be submitted to the National Library of Medicine’s PubMed Central to be made available publicly. Costs for this are provided by PCORI.

15.3.3 Presentations and PCORI-initiated Events

We will attend PCORI meetings or other events to present research findings as requested by PCORI. Expenses for these trips will be covered by PCORI.

15.3.4 Other public and professional dissemination

Our imperative will be to provide any useful information to the care systems, insurers, and other organizations that want to improve the effectiveness, efficiency, and patient-centeredness of their own care coordination efforts. Most of these organizations in the MN area are active collaborators in the proposed study, so they are very interested in using the findings. Most importantly, the HCH Program will certainly put the lessons to use in their certification and recertification relationships with all certified HCH clinics and those applying for certification in the future. Besides individual contacts and visits, this program also has an annual learning day event that brings together representatives from all certified clinics and this topic will be a major focus for these events during and after the grant. ICSI (our regional quality improvement organization with most payors as sponsors and most large care systems as members) has many ways to communicate with most of the clinics in the region (bordering states as well as MN), and because they are also a founding member of the Network for Regional Healthcare Improvement (30 member organizations nationally), they will be able to disseminate the lessons widely.

Finally, we expect that our health system and state government collaborators will be eager to make use of the lessons that they have been part of producing. Hopefully, that will include modifications in the

current rules for clinic certification as well as better payment for the most effective kinds of care coordination.

17.1 Appendix A: Patient data specifications

These data specifications are for identification of patient cohorts as described in Section 5.1.1. Cohort-specific requirements are identified throughout. Data were collected at two separate timepoints most proximal to each cohort's care coordination index date range.

Clinical Data Preparations

Step 1: Identify those patients 18 years of age and older who had a first-ever care coordination start/enrollment date in your care system as follows:

- Historical Cohort: patients with start/enrollment date between 01/01/2018 to 02/28/2019
- Primary Cohort: patients with start/enrollment date between 01/01/2021 to 12/31/2021

Step 2: Pull the clinical data elements from your electronic systems and prepare two data files as specified in the tables below. Submit the data files during the following data submission periods by cohort:

- Historical Cohort data submission period: 06/14/2021 to 08/15/2021
- Primary Cohort data submission period: 3/15/2022 to 5/15/2022

Care Coordination Definitions

Please use the guidance below for identifying patients for the study.

- **Historical Cohort Enrollment Start Date:** Please include patients whose first-ever care coordination enrollment started in your care system between 1/1/2018 – 2/28/2019. Please exclude patients whose care coordination began within your care system before 1/1/2018.
- **Primary Cohort Enrollment Start Date:** Please include patients whose first-ever care coordination enrollment started in your care system between 01/01/2021 – 12/31/2021. Please exclude patients whose care coordination began within your care system before 01/01/2021. Please include patients whose status is deceased but who were enrolled in care coordination during the specified time.
- **Time in Care Coordination:** The study is intended to include patients who were enrolled in care coordination and engaged for a meaningful period of time, using whatever criteria make the most sense in your care system. Please do not include patients who were temporarily or “partially” enrolled. For example, some medical groups may apply an inclusion criterion to their query such as: include only patients who were enrolled for at least 2 months with at least 3 care coordination encounters within the care system. You may also use other ways to narrow the list to those enrolled patients intended for the study, depending on what parameters are used to define a “fully enrolled” care coordination patient in your system.

➤ **Exclusions:** Please apply any appropriate research exclusion lists to exclude patients who have opted out of research in your organization.

Summary of Changes for Primary Cohort

We had hoped to have few changes for this data submission but concluded that expanding the number of data points for three quality measures to include the following data would greatly improve the ability to measure changes in care quality from care coordination. If you have any questions or concerns about adding these data, please contact [contact].

- File 3: All HbA1c tests obtained during the specified time period (see below).
- File 4: All blood pressures obtained during the specified time period (see below).
- File 5: All height and weight values obtained during the specified time period (see below). Used for calculating BMI.

Questions? Please visit the [MNCARES Information Page](#) for answers to common questions or contact us at [contact].

Data Elements & Field Specifications – Files 1-5

File 1: Patient Demographic, Care Coordination Enrollment, Encounter Data

Element Order	Field Name	Details	Required or Situational*	Format/Field Length	Error Causes
A	Patient ID	Enter the patient ID that is submitted for clinical quality data submission to MNCM. If your clinic has not submitted MRNs or a unique patient ID in past submissions, please contact [contact] 
• Unique patient identifier for clinic.• DO NOT enter an SSN.	R	String; up to 50 characters	Blank fields
B	Patient First Name	Enter the first name of the patient.	R	Text	Blank fields
C	Patient Middle Name	Please enter the patient's middle name or initial if it is recorded in the medical record.	S	Text	
D	Patient Last Name	Enter the last name of the patient.	R	Text	Blank fields
E	Patient Master Index (PMI)	This is a unique patient identification number that the Department of Human Services uses for previous and current Minnesota Health Care Program participants.	S	String; up to 50 characters	

Element Order	Field Name	Details	Required or Situational*	Format/Field Length	Error Causes
F	Current Primary Insurance Member ID	Enter the most recent Member ID on file as of the date of the data pull. 
 • Unique patient identifier for health plan • Do NOT enter an SSN; instead, enter "999" 	R	String; up to 50 characters	Blank fields
G	Current Primary Insurance	Enter the most recent primary insurance on file as of the date of the data pull. Please refer to a separate document entitled Insurance Coverage Data Elements, Field Specifications & Codes for field specifications.	R	Number; up to 2 digits	Blank fields Values outside allowable range
H	Current Subscriber name	Enter the full name for the person that subscribes to the health plan.	S	Text	
I	Prior Primary Insurance Member ID	Enter the previous Member ID on file if obtainable. 
 • Unique patient identifier for health plan • Do NOT enter an SSN; instead, enter "999". 	S	String; up to 50 characters	
J	Prior Primary Insurance	Please refer to a separate document entitled Insurance Coverage Data Elements, Field Specifications & Codes for field specifications.	S	Number; up to 2 digits	Values outside allowable range
K	Prior Subscriber name	Enter the full name for the person that subscribed to the prior health plan.	S	Text	
L	Patient Date of Birth (DOB)	Must be age 18 years or older as of the start/enrollment date of care coordination (per AG below).	R	mm/dd/yyyy or m/d/yyyy	Blank fields
M	Patient Sex	F = Female M = Male U = Unknown/Undefined	R	Text; 1 character	Blank fields Values outside allowable range
N	Patient Date of Death (DOD)		S	mm/dd/yyyy or m/d/yyyy	
O	Patient Status	Enter the most recent patient status at the time of the data pull. 0 = Deceased 1 = Alive	S	Number; 1 digit	

Element Order	Field Name	Details	Required or Situational*	Format/Field Length	Error Causes
P	Race1	Enter the code that corresponds to the patient reported race. For patients who report more than one race, enter one code per field for each reported race, up to five. Do not submit the same code in multiple fields. 1 = American Indian or Alaska Native 2 = Asian 3 = Black or African American 5 = Native Hawaiian/Other Pacific Islander 6 = White 7 = Some other race/Patient does not identify with any of the race categories provided. 97 = Patient actively chose not to disclose/declined 98 = Patient reports that race is unknown. If patient was not asked for their race or if race was left blank by patient, leave the fields blank.	S	Number; up to 2 digits	Values outside allowable range
Q	Race2		S	Number; up to 2 digits	
R	Race3		S	Number; up to 2 digits	
S	Race4		S	Number; up to 2 digits	
T	Race5		S	Number; up to 2 digits	
U	Ethnicity	Enter the code that corresponds to the patient-reported ethnicity 4 = Hispanic or Latino 8 = Not Hispanic or Latino 97 = Patient actively chose not to disclose/declined 98 = Patient reports that ethnicity is unknown If patient was not asked for their ethnicity or if ethnicity was left blank by patient, leave the field blank.	S	Number; up to 2 digits	Values outside allowable range
V	Preferred Language	Enter the code that corresponds to the patient-reported preferred language. Please refer to a separate document entitled RELC Data Elements, Field Specifications & Codes for coding table. Additional options include: 97 = Patient actively chose not to disclose/declined 98 = Patient reports that preferred language is unknown. 99 = Patient reported preferred language does not match one of the available codes. Enter name of preferred language in Preferred Language Other field. If patient was not asked for their preferred language or if preferred language was left blank by patient, leave the fields blank.	S	Number; up to 2 digits	Values outside allowable range
W	Preferred Language Other	If Element Position V = 99, submit preferred language.	S	String; up to 50 characters	
X	Country of Origin	Enter the code that corresponds to the patient-reported country of origin. Please refer to a separate document entitled RELC Data Elements, Field Specifications & Codes for coding table. Additional options include:	S	Number; up to 3 digits	Values outside

Element Order	Field Name	Details	Required or Situational*	Format/Field Length	Error Causes
		
997 = Patient actively chose not to disclose/declined 998 = Patient reports that country of origin is unknown. 999 = Patient reported country of origin does not match one of the available codes. Enter name of country of origin in Country of Origin Other field. If patient was not asked for their country of origin or if country of origin was left blank by patient, leave the fields blank.
			allowable range
Y	Country of Origin Other	If Element Position X = 999, submit country of origin.	S	String; up to 50 characters	
Z	Street Address	Patient's primary residence	R	String; up to 50 characters	Blank fields
AA	City	Patient's primary residence	R	String; up to 50 characters	Blank fields
AB	State	Standard two-character state abbreviation Patient's primary residence	R	Text; 2 characters	Blank fields
AC	ZIP Code	Minimum of five digits Patient's primary residence	R	Number	Blank fields Values with less than five digits
AD	Primary Phone Number	Minimum of 10 digits	R	Number	
AE	Secondary Phone Number	Minimum of 10 digits	S	Number	
AF	Interpreter needed?	0 = No 1 = Yes	S	Number	
AG	Start/enrollment date of care coordination	Enter the date that corresponds to the start of the patient's care coordination enrollment between 1/1/2018-2/28/2019 (Historical Cohort) and 1/1/2021 – 12/31/2021 (Primary Cohort). 
 The start date should represent the patient's first-ever enrollment in care coordination in your care system Exclude patients whose care coordination began within your care system before 1/1/2018 (Historical Cohort) or 1/1/2021 (Primary Cohort). 	R	mm/dd/yyyy or m/d/yyyy	Blank fields

Element Order	Field Name	Details	Required or Situational*	Format/Field Length	Error Causes
		
 Only include care coordination patients that were engaged for a meaningful period of time as defined as Time in Care Coordination above. 			
AH	Clinic ID from the start of care coordination enrollment	Enter the MNCM-assigned clinic ID associated with the start of the patient's care coordination enrollment.	R	Number; up to 4 digits	Blank fields
AI	Date of most recent care coordination encounter	
 Enter the date that corresponds with the patient's most recent care coordination encounter. This date can occur any time up until the data is pulled. If patient did not have any subsequent care coordination encounters after the initial start/enrollment encounter, enter the start/enrollment care coordination date from AG. 
Type of encounter may be any of the following: office, phone, video, or home visit.
	S	mm/dd/yyyy or m/d/yyyy	
AJ	Clinic ID from the most recent care coordination encounter	Enter the MNCM-assigned clinic ID associated with the patient's most recent care coordination encounter.	S	Number; up to 4 digits	
AK	Date of most recent encounter	
 Enter the most recent ambulatory encounter date, regardless of whether the visit was a care coordination visit. This date can occur any time up until the data is pulled. If patient did not have any subsequent encounters after the initial start/enrollment encounter, enter the date of start/enrollment care coordination date from AG. Type of encounter may be any of the following: office, phone, video, or home visit. 	S	mm/dd/yyyy or m/d/yyyy	
AL	Clinic ID from most recent encounter	Enter the MNCM-assigned clinic ID associated with the most recent ambulatory encounter.	S	Number; up to 4 digits	
AM	Count of care coordination encounters	
 Count of all care coordination encounters between the patient's start date (AG) and most recent care coordination encounter (AI). This count should include the initial start/enrollment date and the most recent care coordination encounter. If patient did not 	S	Number; up to 3 digits	

Element Order	Field Name	Details	Required or Situational*	Format/Field Length	Error Causes
		
have any subsequent encounters after the initial start/enrollment encounter, enter “1”.
 
 Type of encounter may be any of the following: office, phone, video, or home visit. 			

* Both Required (R) and Situational (S) data are relevant to and important for the study. Required data must be submitted and cannot be blank.

Situational data is submitted if the clinic collects and can extract or obtain the information from their record system. Submit data for those patients when the information is available (e.g., secondary phone number). If the data was not collected or is not obtainable, the field can be left blank.

File 2: Diagnosis Codes from Patient's Active Problem List

Element Order	Field Name	Details	Required or Situational*	Format/Field Length	Error Causes
A	Patient ID	
Enter the Patient ID that was submitted in File 1.
 
 Unique patient identifier for clinic. DO NOT enter an SSN. 	R	String; up to 50 characters	Blank fields
B	Clinic ID from the start of care coordination enrollment	Enter the MNCM-assigned clinic ID associated with the start of the patient's care coordination enrollment. This is the same ID entered in the Demographic file, element order AH.	R	Number; up to 4 digits	Blank fields
C-AZ	Diagnosis Codes from Patient's Active Problem List	
Enter all diagnosis codes (e.g., ICD-10) associated with the patient's active problem list. This includes diagnoses unrelated to the care coordination.
 
 All applicable characters, including decimals (e.g., E11.9) Up to 50 diagnoses may be submitted One code per field 	R	String; up to 50 characters	Blank fields

* Both Required (R) and Situational (S) data are relevant to and important for the study. Required data must be submitted and cannot be blank.

Situational data is submitted if the clinic collects and can extract or obtain the information from their record system. Submit data for those patients when the information is available (e.g., secondary phone number). If the data was not collected or is not obtainable, the field can be left blank.

File 3 (Primary Cohort only): HbA1c Tests

Contains all tests obtained or documented in the medical record from 01/01/2020 through the date of the data pull. One test per row. Tests from outside providers that are documented in the patient record may also be included.

Element Order	Field Name	Details	Required or Situational*	Format/Field Length	Error Causes
A	Patient ID	Enter the Patient ID that was submitted in File 1. 
• Unique patient identifier for clinic.• DO NOT enter an SSN.	R	String; up to 50 characters	Blank fields
B	HbA1c Date	Enter the date of the HbA1c test.	R	mm/dd/yyyy or m/d/yyyy	Blank fields
C	HbA1c Value	Enter the value of the HbA1c test result. Include decimals. If the result was too high to calculate, leave blank.	S	Number	

* Both Required (R) and Situational (S) data are relevant to and important for the study. Required data must be submitted and cannot be blank. Situational data is submitted if the clinic collects and can extract or obtain the information from their record system. Submit data for those patients when the information is available (e.g., secondary phone number). If the data was not collected or is not obtainable, the field can be left blank.

File 4 (Primary Cohort only): Blood Pressures

Contains all blood pressures obtained or documented in the medical record from 01/01/2020 through the date of the data pull. Include readings from eligible specialties below. For multiple readings at one encounter, submit all recorded readings, one per row. Results from outside providers that are documented in the patient record may also be included. Blood pressures that are taken by the patient on a digital device in the context of a virtual (online or telephone) visit are acceptable.

Eligible Specialties:

- Family Medicine
- Internal Medicine
- Geriatric Medicine
- Cardiology
- Endocrinology

Do not include results:

- Taken during an acute inpatient stay or an ED visit.
- Taken during an outpatient visit which was for the sole purpose of having a diagnostic test or surgical procedure performed.
- Taken the same day a major diagnostic or surgical procedure.

Element Order	Field Name	Details	Required or Situational*	Format/Field Length	Error Causes
A	Patient ID	Enter the Patient ID that was submitted in File 1. 
• Unique patient identifier for clinic.• DO NOT enter an SSN.	R	String; up to 50 characters	Blank fields
B	Blood Pressure Date	Enter the date of the blood pressure result.	R	mm/dd/yyyy or m/d/yyyy	Blank fields
C	Systolic Value	Enter the value of the systolic reading.	R	Number	Blank fields
D	Diastolic Value	Enter the value of the diastolic reading	R	Number	Blank fields

* Both Required (R) and Situational (S) data are relevant to and important for the study. Required data must be submitted and cannot be blank.

Situational data is submitted if the clinic collects and can extract or obtain the information from their record system. Submit data for those patients when the information is available (e.g., secondary phone number). If the data was not collected or is not obtainable, the field can be left blank.

File 5 (Primary Cohort only): Height and Weight

Contains all heights and weights obtained or documented in the medical record from 01/01/2020 through the date of the data pull. One height and weight per row.

Element Order	Field Name	Details	Required or Situational*	Format/Field Length	Error Causes
A	Patient ID	Enter the Patient ID that was submitted in File 1. 
 • Unique patient identifier for clinic. • DO NOT enter an SSN. 	R	String; up to 50 characters	Blank fields
B	Encounter Date	Enter the date of the encounter where height/weight was obtained by clinical staff.	R	mm/dd/yyyy or m/d/yyyy	Blank fields
C	Height	Enter the value of the patient's height (inches, including decimals if applicable).	S	Number	
D	Weight	Enter the value of the patient's weight (pounds, including decimals if applicable).	S	Number	

* Both Required (R) and Situational (S) data are relevant to and important for the study. Required data must be submitted and cannot be blank.

Situational data is submitted if the clinic collects and can extract or obtain the information from their record system. Submit data for those patients when the information is available (e.g., secondary phone number). If the data was not collected or is not obtainable, the field can be left blank.

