7.3.6.2 Population used to generate effect estimates

As described in Section 4.2.2, patients will be eligible for analyses if they have been designated for care coordination at a participating clinic and have not opted out of research. For utilization outcomes, inclusion will additionally require health insurance coverage from a participating payor. For patient-reported outcomes, inclusion will additionally require completion of the study survey. As described above, patients will be followed for health care quality and utilization outcomes over the 12 months preceding and the 12-36 months following the first observed enrollment in care coordination, and patient-reported outcomes will be collected by survey in the 6-18 months following first enrollment in care coordination (Primary Cohort only). For a discussion of analytic implications of selection by survey response, please see Section 7.3.6.1 above. Differences in survey respondents vs. non-respondents will be assessed for potential selection bias and potential impact on validity of results.

7.3.6.3 Timing of the outcome assessment relative to the initiation and duration of exposure

As described above, timing in the assessment of health care quality and utilization outcomes will account for outcomes in the 12 months preceding initiation of care coordination in comparison to outcomes in the 12 months following initiation of care coordination. Assessment of patient-reported outcomes will be collected in the 6-18 months following initiation of care coordination (Primary Cohort only). Patients' exposure time will be the observable duration of time spent in a care coordination program; they will be considered exposed for the entire follow-up period for each outcome. Exposure to the intervention (care coordination) will be determined at the patient level, whereas comparator status (choice of care coordination model) will be implemented by each clinic at the clinic level. Due to these conditions, sequential temporality will be ensured, and immortal time bias will not be applicable.

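### The instruction to list deceased patients is written for the Primary Cohort only, so the Historical Cohort, listed 27.5 to 43.4 months after start, may be partly selected for survival, unevenly by care system

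*Combined protocol and SAP*

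**What the plan says.** Appendix A (17.1), under Care Coordination Definitions, gives each cohort its own inclusion bullet.

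- Historical Cohort: "Please include patients whose first-ever care coordination enrollment started in your care system between 1/1/2018 – 2/28/2019". The only exclusion in the bullet is "Please exclude patients whose care coordination began within your care system before 1/1/2018". Vital status is not mentioned.
- Primary Cohort: the same structure with 2021 dates, plus a closing sentence: "Please include patients whose status is deceased but who were enrolled in care coordination during the specified time".

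The appendix opens by saying "Cohort-specific requirements are identified throughout". The submission windows are "Historical Cohort data submission period: 06/14/2021 to 08/15/2021" and "Primary Cohort data submission period: 3/15/2022 to 5/15/2022".

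File 1, used for both cohorts, has a date-of-death field (N) and a status field (O, 0 = deceased, 1 = alive) with the instruction "Enter the most recent patient status at the time of the data pull". Both are situational fields and may be blank. The appendix also lets each system use its own criteria for who counts as fully enrolled.

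Section 7.3.6.3 says that "immortal time bias will not be applicable", arguing from how exposure and comparator status are assigned. Section 7.3.1 replicates Aim 1 in both cohorts and then pools them to test the cohort-by-model interaction. It also plans 1-, 2- and 3-year Historical outcomes where data exist. Section 9.1, on missing data, does not name death.

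**The concern.** The instruction is absent for the cohort with the longer gap between start and listing. If cohort-specific requirements are marked as such, a programmer in a care system can fairly take a sentence in one bullet as applying to that bullet alone. A query built on an active-patient table would drop people who died before mid-2021, and a blank situational field would not reveal it.

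A Historical patient listed only because he or she was alive in mid-2021 is guaranteed to have survived the 12-month outcome window. Since the shortest gap is 27.5 months, survival through the 2-year window is also guaranteed; for those who started at least 36 months before the pull, so is survival through the 3-year window. If people near death use more hospital and emergency care, both primary outcomes, a living-only list understates Historical utilization. Quality measures could be affected as well.

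Listing was done by many separate care systems, so practice could vary between them. The cohort-by-model interaction would then compare a Primary Cohort that includes deaths with a Historical Cohort that includes them in some systems and not in others.

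**Working it through.** **Inputs from the plan.** Start dates and submission windows: Appendix A. Historical size: 329 clinics, 66 patients per clinic, about 45% (30) with payor data, intra-cluster correlation 0.01 (Section 7.2.2). Primary size: 57 per clinic over 12 months (Section 7.2.1). The plan gives no mortality rate; 2%, 5% and 10% a year are assumed.

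**The plan's own figures.** 57 × 14/12 = 66.5 (stated 66). 0.45 × 66 = 29.7 (stated 30). Planned Historical total: 329 × 66 = 21,714.

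**Gap from start to listing**, taking the pull to fall inside the submission window, at 30.4375 days per month:

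- Historical, shortest: 28 Feb 2019 to 14 Jun 2021 = 837 days = 27.5 months. Longest: 1 Jan 2018 to 15 Aug 2021 = 1,322 days = 43.4 months.
- Primary, shortest: 31 Dec 2021 to 15 Mar 2022 = 74 days = 2.4 months. Longest: 1 Jan 2021 to 15 May 2022 = 499 days = 16.4 months.

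**Share dead by listing** = 1 − (1 − r)^(t/12), with r the annual mortality and t averaged uniformly over the gap:

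| Assumed r | Historical | Primary | Historical patients lost if every system dropped its dead |
|---|---|---|---|
| 2% | 5.8% | 1.6% | 1,258 of 21,714 |
| 5% | 14.1% | 3.9% | 3,051 |
| 10% | 26.7% | 7.9% | 5,797 |

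**Precision.** With design effect 1 + (m − 1) × 0.01, even that worst case raises the minimum detectable difference only by a factor of 1.02 to 1.10 at 66 per clinic, and 1.02 to 1.13 at 30. The issue is selection, not power.

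**Effect on the 12-month mean rate.** Let q be the share of starters with excess use and R their rate ratio against everyone else. Omitting them lowers the mean by 1 − 1/(1 − q + qR). Suppose 15% are dead by listing.

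- Share of those deaths within 12 months of start, at constant mortality: 2/5.8 = 34%, 5/14.1 = 35%, 10/26.7 = 37%.
- If excess use is confined to those deaths, q = 0.15 × 0.355 = 0.053. With R = 2 the drop is 1 − 1/1.053 = 5.0%.
- If the ratio applied to everyone dead by the pull, q = 0.15 and the drop would be 1 − 1/1.15 = 13.0%.

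**Carry-over to the model comparison.** This needs a further assumption. If the share of patients from living-only systems differed by 30 percentage points between models, the artificial difference would be about 0.30 × 5.0% = 1.5% (0.30 × 13.0% = 3.9% on the wider reading). Section 7.2.2 says most scenarios can detect a 10% difference.

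**The case against.** The strongest reply is that the Historical text already covers the dead. Step 1 and the Historical bullet ask for everyone whose first enrollment fell in the window. The stated exclusions are an earlier start, partial enrollment and research opt-out; none concerns vital status. Local discretion is about what counts as full enrollment. File 1 carries the death fields without restriction, whereas Files 3 to 5 are marked for the Primary Cohort only, and the summary of changes for the Primary Cohort mentions only those three files. The sentence on deceased patients can therefore be read as a clarification. A date of death also could not be a required field, because required fields cannot be blank.

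All of this stands. A reader might infer that the plan excludes deceased Historical patients, or that the two cohorts are not comparable. The documents support neither: they contain no such exclusion, and nothing shows that any system omitted deaths. What remains is that the sponsor found the sentence worth writing for the shorter gap and did not write it for the longer one. Nothing in the analysis plan would show whether systems read the silence differently.

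Two further replies also have force. Care model is classified clinic by clinic, and the organizational survey allows for systems with both kinds of clinic, so uneven listing by system need not become a difference between models. The planned use of each patient's 12 months before start may absorb part of any difference in utilization. The main Aim 1 question also rests on the Primary Cohort, where the instruction is explicit.

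**Conclusion.** The point holds as an asymmetric instruction that permits survivor selection in the Historical Cohort, not as a demonstrated exclusion or bias. The gaps of 27.5 to 43.4 and 2.4 to 16.4 months follow from the plan's dates. The shares dead by listing (about 6% to 27% Historical, 2% to 8% Primary) rest on assumed annual mortality of 2% to 10%.

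The size of any distortion in 12-month rates is uncertain. A reader might take the 13% drop and the roughly 4% difference between models as the likely effect. Both apply excess use to every death up to the pull, although only about a third would fall inside the 12-month window; the between-model figure also needs an imbalance for which the documents give no evidence. Confining excess use to deaths within 12 months gives about 5% for a living-only list, and that too rests on assumed inputs.

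The results at risk are Historical utilization and quality, including the 2- and 3-year outcomes, and the pooled interaction. The Primary Cohort analysis on its own is not affected.

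**What to change.** 1. State in Appendix A and Section 4.2.2 that the inclusion rule is the same for both cohorts: all qualifying starters, whether or not they have since died. The Historical window closed in August 2021, so this sentence alone changes no data.
2. Tabulate File 1 fields N and O by care system, care model and cohort. Count blanks separately, since a blank is not evidence of no deaths. Ask systems with no recorded Historical deaths how they built their query.
3. Run the Historical utilization and quality analyses, and the pooled interaction, with and without systems that listed only living patients or whose practice cannot be confirmed.
4. Qualify Section 7.3.6.3 to say that its statement on immortal time does not cover survival to listing in the Historical Cohort.

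Resubmission of omitted patients is optional. It would mean repeating payor verification, claims extraction and linkage, and Section 13.4.3 has the identity crosswalk destroyed within 6 months of completing the linked databases.

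The cost is one tabulation, queries to some systems, and a smaller Historical sample in the sensitivity analysis.
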